Appendix B: ECOG Performance Status Scale

SCORE	DESCRIPTION
0	Fully active, able to carry on all pre-disease performance without restriction.
1	Restricted in physically strenuous activity but ambulatory and able to carry out work of a light or sedentary nature, e.g., light house work, office work.
2	Ambulatory and capable of all self-care but unable to carry out any work activities. Up and about more than 50% of waking hours.
3	Capable of only limited self-care, confined to bed or chair more than 50% of waking hours.
4	Completely disabled. Cannot carry on any self-care. Totally confined to bed or chair.
5	Dead.

Appendix C: NCI CTCAE Version 5.0

Toxicity will be scored using NCI CTCAE Version 5.0 for toxicity and adverse event reporting. A copy of the NCI CTC Version 5.0 can be downloaded from the CTEP homepage: (https://ctep.cancer.gov/protocolDevelopment/electronic_applications/ctc.htm). All appropriate treatment areas have access to a copy of the CTCAE Version

Appendix D: International Workshop Response Criteria (IWRC) for Non-Hodgkin's Lymphoma

Complete Response (CR)

Complete disappearance of all detectable clinical and radiographic evidence of disease and disappearance of all-disease related symptoms if present before therapy, and normalization of those biochemical abnormalities (e.g., lactate dehydrogenase [LDH] definitely assignable to NHL).

All lymph nodes and nodal masses must have regressed to normal size ($\square 1.5$ cm in their greatest transverse diameter for nodes > 1.5 cm before therapy). Previously involved nodes that were 1.1 to 1.5 cm in their greatest transverse diameter before treatment must have decreased to $\square 1$ cm in their greatest transverse diameter after treatment, or by more than 75% in the sum of the products of the greatest diameters (SPD).

The spleen, if considered to be enlarged before therapy on the basis of a CT scan, must have of the difficulties in accurately evaluating splenic and hepatic size. For instance, spleens thought to be of normal size may contain lymphoma, whereas an enlarged spleen may not necessarily reflect the presence of lymphoma but variations in anatomy, blood volume, the use of hematopoietic growth factors, or other causes. The determination of splenic volume or splenic index by CT scan is cumbersome and not widely used. Any macroscopic nodules in any organs detectable on imaging techniques should no longer be present. Similarly, other organs considered to be enlarged before therapy due to involvement by lymphoma, such as liver and kidneys, must have decreased in size.

If the bone marrow was involved by lymphoma before treatment, the infiltrate must be cleared on repeat bone marrow aspirate and biopsy of the same site. The sample on which this determination is made must be adequate (>20 mm biopsy core). Flow cytometric, molecular, or cytogenetic studies are not considered part of routine assessment to document persistent disease at the present time.

Complete Response/Unconfirmed (CRu)

CR/unconfirmed (CRu) includes those subjects who fulfill criteria 1 and 3 above, but with one or more of the following features:

A residual lymph node mass greater than 1.5 cm in greatest transverse diameter that has regressed by more than 75% in the SPD. Individual nodes that were previously confluent must have regressed by more than 75% in their SPD compared with the size of the original mass.

Indeterminate bone marrow (increased number or size of aggregates without cytological or architectural atypia).

Partial Response (PR)

>50% decrease in SPD of the six largest dominant nodes or nodal masses. These nodes or masses should be selected according to the following features: (a) they should be clearly measurable in at least two perpendicular dimensions, (b) they should be from as disparate regions of the body as possible, and (c) they should also include mediastinal and retroperitoneal areas of disease whenever these sites are involved.

No increase in the size of the other nodes, liver, or spleen.

Splenic and hepatic nodules must regress by at least 50% in the SPD.

With the exception of splenic and hepatic nodules, involvement of other organs is considered assessable and not measurable disease.

Bone marrow assessment is irrelevant for determination of a PR because it is assessable and not measurable disease; however, if positive, the cell type should be specified in the report, e.g., large-cell lymphoma or low-grade lymphoma (i.e., small, lymphocytic small cleaved, or mixed small and large cells.)

No new sites of disease.

Stable Disease (SD)

Stable disease is defined as less than a PR (see above) but is not progressive disease (see below).

Relapsed Disease (RD)

Appearance of any new lesion or increase by >50% in the size of previously involved sites. (only applies to subjects that achieve a CR).

>50% increase in greatest diameter of any previously identified node greater than 1 cm in its short axis or in the SPD of more than one node.

Progressive Disease (PD)

>50% increase from nadir in the SPD of any previously identified abnormal node for PRs or nonresponders.

Appearance of any new lesion during or at the end of therapy which is >1.5 cm by radiologic evaluation or greater than 1 cm by physical examination

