Desquamating (blistering) rash- any Grade	
 Discontinue lenalidomide. Remove patient from study. 	
 Discontinue lenalidomide. Remove patient from study.

Table 2: Lenalidomide Dose Modifications

NCI CTC Toxicity Grade	Onset Day 2-21 of Cycle	Onset \geq Day 22 of Cycle
Neuropathy Grade 3	
 Hold (interrupt) lenalidomide dose. Follow at least weekly. If the toxicity resolves to \leq grade 1 prior to Day 21, restart lenalidomide at next lower dose level and continue the cycle through Day 28. 	
 Omit lenalidomide for the remainder of the cycle. See Instructions for Initiation of a New Cycle and reduce the dose of lenalidomide by 1 dose level.
Grade 4	
 Discontinue lenalidomide. Remove patient from study. 	
 Discontinue lenalidomide. Remove patient from study.
Venous thrombosis/embolism \geq Grade 3	
 Hold (interrupt) lenalidomide and start anticoagulation; restart lenalidomide at investigator's discretion (maintain dose level). 	
 Omit lenalidomide for remainder of cycle.
Hyperthyroidism or hypothyroidism	
 Omit lenalidomide for remainder of cycle, evaluate etiology, and initiate appropriate therapy. See Instructions for Initiation of a New Cycle and reduce the dose of lenalidomide by 1 dose level. 	
 Omit lenalidomide for remainder of cycle, evaluate etiology, and initiate appropriate therapy. See Instructions for Initiation of a New Cycle and reduce the dose of lenalidomide by 1 dose level.
other non-hematologic toxicity \geq Grade 3 attributable to lenalidomide	
 Hold (interrupt) lenalidomide dose. Follow at least weekly. If the toxicity resolves to \leq grade 2 prior to Day 21, restart lenalidomide at next lower dose level and continue the cycle through Day 28. 	
 Omit lenalidomide for remainder of cycle. See Instructions for Initiation of a New Cycle and reduce the dose of lenalidomide by 1 dose level.

NOTE: If subjects do not have adequate hematological recovery within 28 days of their last study treatment, lenalidomide will be discontinued and not restarted. However, the subjects will still be followed for response assessment and included in endpoint analyses.

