6.3.4 Prohibited concomitant therapy

Concomitant use of sargramostim (GM-CSF), other anti-cancer therapies, including radiation, thalidomide, or other investigational agents is not permitted while subjects are receiving study drug during the treatment phase of the study.

7 Response Definition (see Appendix D + E)

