7.6 Progressive Disease (PD)

- 7.6.1 $\geq 50\%$ increase from nadir in the SPD of any previously identified abnormal node for PRs or non-responders.
- 7.6.2 Appearance of any new lesion during or at the end of therapy which is > 1.5 cm by radiologic evaluation or greater than 1 cm by physical examination.

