7.9 Time to progression (TTP)

TTP is defined as the time from the first day of protocol therapy to the first event defining progression of disease or last subject contact. TTP is defined for all subjects receiving protocol therapy, following an intent-to-treat analysis plan. TTP from rituximab is defined for patients receiving rituximab (Part II) from the first day of rituximab therapy to the first event defining treatment failure.

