Appendix E: Response Criteria for NHL

RESPONSE CRITERIA FOR LYMPHOMA

Response Category	Physical Examination	Lymph Nodes	Lymph Node Masses	Bone Marrow
CR	Normal	Normal	Normal	Normal
CRu	Normal	Normal	Normal	Indeterminate
	Normal	Normal	> 75% decrease	Normal or indeterminate
PR	Normal	Normal	Normal	Positive
	Normal	≥ 50% decrease	≥ 50% decrease	Irrelevant
	Decrease in liver/spleen	≥ 50% decrease	≥ 50% decrease	Irrelevant
Relapse/Progression	Enlarging liver/spleen, new sites	New or increased	New or increased	Reappearance

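### Sections 7.6.2 and Appendix D stop counting new lesions as progression once therapy ends, Appendix E does not, so TTP and PFS events after treatment are ambiguous for PR and SD subjects

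*Combined protocol and SAP*

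**What the plan says.** - **Section 7.6.2 and Appendix D (PD).** Both give the new-lesion criterion as "Appearance of any new lesion during or at the end of therapy which is" above 1.5 cm on imaging or 1 cm on examination.
- **Section 7.6.1 (PD).** The other criterion is a 50% "increase from nadir in the SPD of any previously identified abnormal node for PRs or non-responders". It has no time limit but concerns only nodes already identified.
- **Section 7.5.1 and Appendix D (RD).** Any new lesion counts, with no time limit, but the rule "only applies to subjects that achieve a CR".
- **Appendix E.** The heading of Section 7 refers to Appendices D and E together. The Relapse/Progression row of Appendix E lists "Enlarging liver/spleen, new sites" and new or increased nodes and masses. It has no time limit, CR condition or size threshold.
- **Section 7.9.** TTP runs "to the first event defining progression of disease or last subject contact", for all treated subjects. Section 7.10 adds death from any cause for PFS. Neither says which progression definition applies after treatment stops.
- **Section 6.1.3, note to Table 2.** When lenalidomide is permanently stopped for inadequate haematological recovery, "the subjects will still be followed for response assessment and included in endpoint analyses".

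**The concern.** Under 7.5, 7.6 and Appendix D alone, a PR or SD subject who has stopped therapy and then develops a new lesion meets neither the PD nor the RD definition. TTP would run on until a known node grows by 50% or until last contact. Under Appendix E the same lesion is progression on the day it is seen. No rule says which text governs, so two analysts who both follow the protocol could give one subject different TTP dates.

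The error goes one way. Section 8 declares significance if a 95% interval for the ratio of on-study to prior median TTP excludes 1. Leaving out late new lesions lengthens only the on-study median. The documents do not say which criteria date progression on the prior regimen, but eligibility accepts progression within 6 months of any rituximab dose, with no requirement that it occurred on therapy.

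**Working it through.** **Who is affected.** Three conditions must hold together.

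1. Best response is PR or SD (or CRu, if CRu is not read as CR). Subjects in CR are covered by 7.5.1.
2. The subject is off protocol therapy. Under Section 3.1 treatment runs until progression, unacceptable toxicity or withdrawal, so most subjects still at risk are on therapy and 7.6.2 applies in full.
3. The subject is still assessed for response. Scheduled restaging stops at the same three points, and Section 4.4 names only survival data after withdrawal. The one off-drug group expressly kept in response follow-up is that of the Table 2 note.

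The note stops lenalidomide. A Cohort 1 subject may still be taking dexamethasone, and Section 6.1.2 lets cytopenic subjects proceed with rituximab. In Cohort 2 there is no dexamethasone and rituximab is given only in cycle 3, so a subject stopped after cycle 3 is off all protocol therapy and still in the endpoint analyses.

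**Size (illustration).** The plan states no figure that depends on this point. Inputs:

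- n = 45, and on-study median TTP m = 6 or 12 months (both from Section 8).
- Assumed: exponential TTP with hazard λ = ln 2 / m.
- Assumed: a share f of 5% to 30% stop therapy before progression and stay in follow-up, with stopping hazard μ = λf/(1 − f), so that μ/(λ + μ) = f.
- Assumed: a share s of 30% to 50% of their progressions show as a new lesion only.

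If these events are never counted, the share lost is f × s, and the curve of counted events is

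S*(t) = e^(−λt) + s[(1 − e^(−λt)) − (1 − f)(1 − e^(−λt/(1 − f)))].

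The reported median solves S*(t) = 0.5. Check for m = 6, f = 0.30, s = 0.50 at t = 6.62: λt = 0.765, e^(−0.765) = 0.465, e^(−0.765/0.7) = 0.335, so S* = 0.465 + 0.5 × (0.535 − 0.7 × 0.665) = 0.50.

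| f | s | Events lost of 45 | True 6 months reads | True 12 months reads | Too long by |
|---|---|---|---|---|---|
| 5% | 30% | 0.7 | 6.04 | 12.08 | 0.7% |
| 5% | 50% | 1.1 | 6.07 | 12.14 | 1.2% |
| 10% | 30% | 1.4 | 6.09 | 12.18 | 1.5% |
| 10% | 50% | 2.3 | 6.15 | 12.30 | 2.5% |
| 30% | 30% | 4.1 | 6.35 | 12.69 | 5.8% |
| 30% | 50% | 6.8 | 6.62 | 13.24 | 10.4% |

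**Delay instead of loss.** Because 7.6.1 has no time limit, many of these subjects would have an event later. With an assumed exponential lag of median 3 to 6 months to that event (simulation, 2 million subjects per setting):

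- f = 30%, s = 50%: 6 months reads 6.35 to 6.45, and 12 months reads 12.47 to 12.70.
- f = 5%, s = 30%: 12 months reads 12.04 to 12.06, about 0.3% to 0.5% too long.

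**On the ratio.** With the plan's prior median of 3 months and a true on-study median of 6, the ratio of 2.00 would read between 6.04/3 = 2.01 and 6.62/3 = 2.21 under the permanent-loss table.

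A larger f gives more: f = s = 50% takes 6 months to about 7.6. That would need half of all subjects to be off all therapy yet still followed, which the narrow group above does not suggest.

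**The case against.** The strongest reply is that Appendix E already settles the matter. Section 7 cites it, and its Relapse/Progression row counts new sites at any time and in any responder. This stands in part. A reader might infer from 7.6.2 that every new lesion after treatment is excluded from TTP and PFS; the documents do not support that, because one of the two cited appendices includes it. But Appendix E is a summary grid without size limits, while the detailed definition is written out twice with an explicit time limit. The grid does not say that it overrides the definition.

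A reader might also infer that the bias grows with all stopping for toxicity. That is not supported either: scheduled restaging ends at unacceptable toxicity, and only the Table 2 note keeps an off-drug group in response follow-up.

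Three further limits stand. Nodal growth under 7.6.1 counts at any time, so many events are delayed and not lost. Death counts for PFS. TTP measured from rituximab ends at treatment failure, a term not tied to 7.6.2.

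**Conclusion.** The concern holds as a conflict between passages. For PR or SD subjects off protocol therapy and still followed, whether a new lesion is a TTP or PFS event depends on whether 7.6.2 and Appendix D or Appendix E is applied, and the first choice favours the combination.

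The effect is probably small. The top of the range, about 10%, needs 30% of subjects in this position, half of their progressions shown only by a new lesion, and none of those ever counted. With 5% in this position and delayed counting it is well under 1%. These rates, and the exponential form, are assumptions. The TTP figures are an upper guide for PFS. TTP is a secondary objective, so this is a minor point, worth correcting because the correction is nearly free.

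**What to change.** 1. In 7.6.2 and Appendix D, replace the time limit with: *at any time after the first dose of protocol therapy, including follow-up after treatment has stopped*. Keep the size limits.
2. Reconcile the Relapse/Progression row of Appendix E with this text, including the size limits, and say which text governs.
3. State in 7.9 and 7.10 that this rule defines progression for TTP and PFS in all subjects.

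The cost is one phrase in two places, an edit to one table row and one sentence in each of two sections. Subjects on treatment are unaffected, since new lesions during therapy already count. No visits or scans are added; for subjects whose scheduled restaging ends at toxicity or withdrawal, the rewording alone will therefore capture little. The stated TTP may be slightly shorter.

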Appendix E: Response Criteria for NHL

RESPONSE CRITERIA FOR LYMPHOMA

Response Category	Physical Examination	Lymph Nodes	Lymph Node Masses	Bone Marrow
CR	Normal	Normal	Normal	Normal
CRu	Normal	Normal	Normal	Indeterminate
	Normal	Normal	> 75% decrease	Normal or indeterminate
PR	Normal	Normal	Normal	Positive
	Normal	≥ 50% decrease	≥ 50% decrease	Irrelevant
	Decrease in liver/spleen	≥ 50% decrease	≥ 50% decrease	Irrelevant
Relapse/Progression	Enlarging liver/spleen, new sites	New or increased	New or increased	Reappearance

Appendix F: WHO classification of B-NHL

- Chronic lymphocytic leukemia/Small lymphocytic lymphoma
- B-cell prolymphocytic leukemia
- Lymphoplasmacytic lymphoma/Waldenström macroglobulinemia
- Splenic marginal zone lymphoma
- Plasma cell neoplasms
 - Plasma cell myeloma
 - Plasmacytoma
 - Monoclonal immunoglobulin deposition diseases
 - Heavy chain diseases
- Extranodal marginal zone B cell lymphoma (MALT lymphoma)
- Nodal marginal zone B cell lymphoma
- Follicular lymphoma
- Mantle cell lymphoma
- Diffuse large B cell lymphoma
- Mediastinal (thymic) large B cell lymphoma
- Intravascular large B cell lymphoma
- Primary effusion lymphoma
- Burkitt lymphoma/leukemia
- Lymphomatoid granulomatosis

Appendix G: Ann Arbor Staging System of Lymphoma

Stage I

Involvement of a single lymph node region (I) OR involvement of a single extra-lymphatic organ or site (IE).

Stage II

Involvement of two or more lymph node regions on the same side of the diaphragm (II) OR localized involvement of an extra-lymphatic organ or site and of one or more lymph node regions on the same side of the diaphragm (IIE).

Stage III

Involvement of lymph nodes regions on both sides of the diaphragm (III) which may also be accompanied by localized involvement of extra-lymphatic organ or site (IIIE) or by involvement of the spleen (IIIS) or both (IIISE).

Stage IV

Diffuse or disseminated involvement of one or more extra-lymphatic organs or tissues with or without associated lymph node involvement.

Identification of the presence or absence of symptoms should be noted with each stage designation:

A = asymptomatic

B = fever ($>38^{\circ}\text{C}$), drenching night sweats, or weight loss greater than 10% of body weight
